a. When study procedures including analysis of identifiable samples or data involving LSCDVAMC enrolled subjects will be conducted at any site other than the LSCDVAMC please provide the following:

Name and contact information for the site: n/a

Describe the plan for communicating protocol amendments, reports of serious adverse events, reports of unanticipated problems involving risks to subjects or others, interim reports, and DSMB reports to external sites. n/a

* When the LSCDVAMC is considered the coordinating center and the PI the lead investigator on cooperative research or a multi-center trial contact AO/Research [contact].

6. Sponsor or other Support (list industry sponsor, government support, etc.):

VA RRD

Section 3 – Research Design and Procedures

7. Definitions- Provide a list of all abbreviations and specialized terms to be used in this document and their definitions:

Abbreviations / Specialized Terms (Use the Enter key in this column to insert additional abbreviations and their definitions)	Definition
LSCDVAMC	Louis Stokes Cleveland DVA Medical Center
VOR	Vestibulo-ocular reflex
DVA	Dynamic visual acuity

8. Provide a BRIEF SUMMARY of the background for this research. DO NOT CUT and PASTE paragraphs that do NOT summarize the background.

- *Include a critical evaluation of existing knowledge, and specifically identify the information gaps that your protocol is intended to fill.*
- *Refer to appropriate citations in the scientific literature and include your references at the end of this section.*
- *Include the rationale for conducting the research at the VA.*

The overall goals of our research are to understand how the brain processes visual and vestibular signals to drive eye movements and postural reflexes, how these functions are disturbed in neurological diseases, how those disturbances cause functional impairments for patients, and how these problems can be treated. The goal of this project is to test the

efficacy of a custom computer game to induce motor learning in the vestibulo-ocular reflex (VOR) and to obtain preliminary data of its feasibility as a tool for clinical vestibular rehabilitation. Vestibular disorders occur commonly in the general population, including veterans, and they are associated with reduced quality-of-life, disruption of work, and limitations of independence [1-4].

Vestibular rehabilitation is the mainstay of treatment for these conditions [5, 6], but standard therapy has key limitations and cannot be easily customized to each patient's specific level of functional impairment. This project builds on our preliminary work to develop an interactive computer game for customized vestibular rehabilitation in clinical and home settings.

Traditional vestibular rehabilitation [7] and our new approach are based on research regarding vestibular physiology and the plasticity of the VOR[8-12]. The primary function of the VOR is to compensate for head movements by rotating the eyes in the opposite direction to stabilize the retina on the object being viewed. This permits vision to remain clear during movement. When vestibular function is lost due to disease, the VOR no longer functions properly and gaze stability during head movement is lost. Vestibular rehabilitation aims to retrain the VOR by improving the function of the reflex and facilitating the optimization of alternative motor strategies to aid compensation.

Recent work suggests that incremental VOR adaptation may be more effective than single-step adaptation[13]—it may be easier to adapt stepwise to smaller errors than to a large error all at once. This approach involves gradually increasing the amount of scene motion relative to the head as the VOR adapts, always working closer to the current level of function. The ability to adapt the VOR incrementally is a key aspect of our vestibular game, and the effectiveness of this approach for short-term adaptation will be directly tested in Aim 1.

5. Cooksey FS. Rehabilitation in vestibular injuries Proc R Soc Med 1946;39:273-278.

In the first aim, we will test the ability of the game to induce VOR plasticity (to modify the gain of the VOR) in subjects with intact vestibular function. To do this, we will have subjects play the game with a visual condition (background movement that is tied to head velocity) that requires them to make a larger than normal eye movement when the head rotates. Such visual-vestibular mismatch has been shown in the past to lead to an increase in the gain of the VOR, even when tested in the dark. Our hypothesis is that incremental adaptation (increasing the amount of visual-vestibular mismatch gradually in a series of steps) will be more effective in inducing this plasticity, so we will compare the change in gain with this paradigm to that induced by imposing the full amount of visual-vestibular mismatch all at once.

In the second aim, we will obtain preliminary data regarding the efficacy and feasibility of the game for clinical vestibular rehabilitation. Patients with peripheral vestibular hypofunction will play the game with the degree of visual-vestibular mismatch customized for their individual level of impairment. They will provide feedback regarding the game and their tolerance of the playing experience. Each subject will play once a week for four weeks. This will give us preliminary data regarding short-term VOR learning in these patients.

10. Describe the means of analyzing the data and evaluating the results.

- *State the anticipated methods to be used for analysis and interpretation of the data.*
- *The methods must compliment the design of the study and the nature of the data which is being collected.*

Data Analysis: The primary outcome measures for this experiment are the passive and active VOR gains. The VOR gain will be calculated for each subject and condition using an

optimization procedure in MATLAB that fits eye velocity to delayed head velocity. In addition to assessing the slow-phase gain change, we will examine “non-vestibular” components of the post-adaptation eye movements; for example, an increase in saccades during the head rotation (covert saccades) may also contribute to gaze stability.

A secondary measure will be the change in DVA with x1.5 viewing, with the prediction that DVA with the moving scene will improve after the VOR has adapted to that visual-vestibular condition and that the improvement in DVA will correlate with that of the VOR. Pre- and post-adaptation VOR gains will be compared using a paired t-test, employing a power transformation if the assumption of normality is not satisfied. Most of the software that will be required for data analysis has already been written by the PI or other members of the laboratory.

Vestibular patients will complete questionnaires (Dizziness Handicap Inventory, Activity-based Balance Confidence) to assess the extent and functional impact of their symptoms, but these will not be outcome measures for the study.

Subjects will rate their feelings of motion sickness on a 0-10 scale following each playing session.

11. Provide a BRIEF DESCRIPTION of how the estimated number of study subjects needed for this research was determined

- *If this is a quantitative study provide the method of determining sample size estimates.*
- *If multiple studies are planned provide a power analysis or justification for each one.*

This is an unpowered pilot study that is funded under the SPiRE mechanism. The number of subjects was chosen to provide adequate preliminary data to support a funding application for a larger clinical trial.

12. The research involves the following procedures conducted by and for what purpose:

PROCEDURE	PERFORMED BY:		PROCEDURE IS:	
	Research Staff	LSCDVAMC Clinical or Support Staff	Standard of Care*	For Research Purposes Only**
Audiotaping / Videotaping Attach VA Form 10-3203 REQUIRED ONLY FOR IN-PATIENT AND OUT-PATIENT SUBJECTS				
Biopsy				
Blood collection				
Chart review – prospective				
Chart review – retrospective				
Review of existing data (ex: registry, Database , etc.)				

PROCEDURE	PERFORMED BY:		PROCEDURE IS:	
	Research Staff	LSCDVAMC Clinical or Support Staff	Standard of Care*	For Research Purposes Only**
X-ray or Ionizing radiation exposure				
Clinical Tests				
Device implantation				
Drug administration				
EEG, EKG , ECG...etc				
Gene therapy, Genetic analysis				
Pregnancy/Breastfeeding Screening				
Interview, Questionnaire, Diary, Survey (please attach)				
Stool collection, Urine collection, or any Non-surgical Specimen collection				
Surgical procedure or Specimen removal during surgery				
Tissue banking (complete Section 12)				
Use of pre-existing tissues/specimens				
Other (list): measurement of head and eye movements; measurement of visual acuity; exposure to visual stimuli during passive and/or active head movement, including while playing a video game.				

- *Standard of care procedures are procedures performed in the course of normal medical care.
- **Research Procedures are performed for the purposes of this research alone.

13. Please describe the research design and all study related procedures.

- Describe **ALL PROCEDURES ASSOCIATED WITH THIS RESEARCH**. This includes standard of care and research procedures.
- For complex studies please include diagrams and tables. Be sure to describe when each procedure will be performed. Be sure to provide information for **each cohort, including normal controls**.

The hypothesis of the study is that computer-game-based incremental adaptation will induce robust VOR motor learning and will provide an engaging platform for vestibular rehabilitation. The hypothesis will be tested with two specific aims:

Aim 1 (Healthy volunteers) will test the efficacy of our game to elicit VOR motor learning in 18 healthy volunteers with no history of vestibular disease. Each subject will play the game

twice for sessions of 300 trials each (about 30 minutes of game playing). In one of these sessions, the game will be structured to increase VOR gain in a single step and in the other session, the gain increase will be advanced incrementally to the same final target. The hypothesis predicts that the latter paradigm will lead to more efficient learning. The specific procedures for Aim 1 will be as follows:

Each subject will participate in two separate sessions on different days. In one session, the full visual-vestibular mismatch ($\times 1.5$) will be introduced at the start of the game (paradigm A) and in the other session scene motion will be gradually adjusted to adapt the VOR incrementally (paradigm B). Each session will consist of 300 trials. To eliminate an order effect, the paradigm order will be randomized across the group of subjects: half will do paradigm A first, and the other half will begin with paradigm B.

Aim 2 (Vestibular Patients) will test the playing experience of 12 subjects with peripheral vestibular disorders and will obtain preliminary data regarding efficacy and feasibility of the game for clinical vestibular therapy. The experimental protocol will be similar to that of Aim 1 (see above), with recording of both eye and head positions during VOR testing and game playing. The active and passive VOR, as well as DVA, will be recorded before and after the game. For each subject, we will begin by determining the baseline VOR gain. The game will then be played with a scene motion that corresponds to a VOR gain that is 20% higher than the baseline value for active rotation, separately set for each direction of head rotation. For example, if a patient with left vestibular hypofunction has a baseline VOR gain of 0.5 for active turns to the left, then scene motion will be set to $\times 0.6$ viewing (20% higher than 0.5). The subject will play the entire game with this condition, rather than advancing the difficulty as in Aim 1, because in clinical rehabilitation the difficulty is advanced more slowly, in a series of sessions over weeks of therapy.

Data Acquisition: We will record head position using our 3-D magnetic-field coil system, long considered the gold standard for measuring eye and head rotations, due to its accuracy and high signal-to-noise ratio. Our system has large field coils (6 ft cube), which provides an adequate area of homogeneity at the center of the field for head-free recordings. Eye movements will be recorded simultaneously using a lightweight head-mounted video-oculography (VOG) system (IScan) that records 2-D eye position at 240 Hz. Analog VOG pupil-tracking data are saved together with the head coil signals in the same file for reliable synchronization of eye and head. Finally, calibrated head positions will be calculated in real time (via Simulink Real Time) and sent over UDP to the gaming computer to drive scene motion at the specified visual-vestibular mismatch. A computer-generated log file will record data from each trial: instructed direction of head movement; optotype size, orientation, and on-time; the subject's key-press response; and a time-stamp for synchronization with the recorded head and eye position data.

Data Analysis: Data are analyzed using custom programs that are written by the PI and study staff. In some cases, electronic data from head and eye movement recordings will be transported offsite for data analysis using specialized software. The data files to be analyzed will be coded so that they can be reconnected with the correct subject when the data are returned to the LSCDVAMC, but they will not contain other subject identifiers. The code will be stored only at the LSCDVAMC (as per Q56), so there will not be a way to connect data to a specific subject when the data are offsite.

14. Will the research involve the following?

N/A **Chart/Data Review**

Placebo Group	 No  Yes (describe):
Other Control Group	 No  Yes (describe): Note that although healthy individuals without vestibular disease will participate in the study, they will be the subjects of Aim 1, not controls for the vestibular patients of Aim 2 (the two Aims have different objectives).
Randomization	 No  Yes (describe): The only randomization will be the order of the two playing sessions in Aim 1.
Deception	 No  Yes (describe):

15. Does the research involve the use and/or disclosure of Individually Identifiable Health Information in any form or medium?

No Yes If yes, complete the required HIPAA Waiver/Authorization forms.

16. Does the study include the administration of a study agent that does not require FDA approval and does not require an IND (e.g. vitamins, food supplements, isotope tracers, alternative medicines, etc.)?

No Yes -*provide a detailed description of the procedures used to assure patient safety*:

17. Will radioactive material be administered or will subjects be exposed to ionizing radiation?

- *Ex. Radiographic equipment, fluoroscopic equipment, and CT scanners, etc.*

No Yes

18. In your judgment, could the objectives of the research be met in a way that presents less risk to subjects?

No Yes *please explain*:

Section 4 – Subject Selection, Recruitment, and Vulnerable Populations

19. Anticipated duration of entire study reported in years: The study as proposed is expected to last for 6 years (a one-year extension was approved by VA RRD, an additional no-cost extension will be requested to complete enrollment and study procedures, follow-on years for additional data analysis, including preparation of the next funding proposal).

20. Estimated number of subjects to be studied at the LSCDVAMC or charts/records to be reviewed.

- *Provide answers for each cohort including normal controls; (patients, family members, treating physicians,):*

AIM 1: Healthy volunteers: 30 (per the funded protocol, enrollment will be stopped when completed data are obtained for 18 subjects)

AIM 2: Vestibular Patients: 20: (per the funded protocol, enrollment will be stopped when completed data are obtained for 6 subjects with unilateral hypofunction and 6 subjects with bilateral hypofunction)

Note that it may be necessary to enroll more than the targeted number of subjects in order to reach the goals, if some subjects drop out before completing the full study.

21. Estimated number of subjects to be studied or charts/records to be reviewed at all sites

- *Provide answers for each cohort including normal controls; (patients, family members, treating physicians,)*

N/A SINGLE SITE

22. Duration of individual subject participation

Provide answers for each cohort including normal controls; (patients, family members, treating physicians,). Each experimental session is expected to last approximately one hour. Healthy volunteers who are the subjects of Aim 1 will each participate for two recording sessions. Vestibular patients who are the subjects of Aim 2 will each participate for four sessions. Analysis of subjects' data will continue for the duration of the study.

Chart/record review N/A

23. Age range of subjects

- *provide answers for each cohort, including normal controls:*

Adults 18 years or greater

Specific age range (list age range): 18-75

Children –waiver from VACO: **attached** **pending- provide submission date:**

***Contact AO/Research [contact] for guidance..*

24. Which of the following will be recruited or reviewed for this study (check all that apply)?

Veteran Inpatients

Men

Veteran Outpatients

Women

Veteran Families

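### Aim 1 frames B versus A as a comparison of changes in gain and names no model for it; pre-game gain as a covariate would usually tighten the estimate at almost no cost

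*Combined protocol and SAP*

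**What the plan says.** Section 3, item 9 (first aim) states the comparison of the incremental paradigm (B) with the single-step paradigm (A): "so we will compare the change in gain with this paradigm to that induced by imposing the full amount". Item 10 gives the outcomes: "The primary outcome measures for this experiment are the passive and active VOR gains". The only test of gain it names is within a condition: "Pre- and post-adaptation VOR gains will be compared using a paired t-test", with the rider "employing a power transformation if the assumption of normality is not satisfied". No model is given for B against A, and no baseline adjustment appears anywhere in the document.

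Item 13 makes Aim 1 a two-session crossover with randomised order, half the subjects starting with each paradigm and the sessions held on different days. No minimum interval is stated. Item 20 sets the size: "enrollment will be stopped when completed data are obtained for 18 subjects".

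Pre-game measurement is stated outright only for Aim 2, in item 13: "The active and passive VOR, as well as DVA, will be recorded before and after the game". For Aim 1 it is an inference, but a firm one: item 13 calls the two protocols similar, and both the pre/post test and the change in gain require it.

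**The concern.** In a crossover, the between-subject part of gain already cancels when B is compared with A within a subject. Subtracting each session's pre-game gain then does two things. It removes whatever that session's pre and post measurements share, and it adds the measurement error of the pre-game value. A change score fixes the slope of post on pre at 1 whatever the data show. Using the pre-game difference as a covariate estimates that slope, so only the predictable part is removed.

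B against A is the only randomised comparison in the study, and 18 subjects inform it. If the slope is well below 1, a change-score analysis gives away precision that the collected data could supply. The design offers one reason to expect this: both paradigms drive gain towards the same final target, so a session that starts lower has further to move. That is reasoning from the design; the plan gives no figure for it.

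**Working it through.** **Inputs from the plan.** 18 completers, two sessions each, order randomised half and half (items 13 and 20); contrast on change in gain (item 9). Item 11 calls the study unpowered, so there is no planned figure to reproduce.

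**Assumed, because the plan gives no value.** Exactly 9 completers per order. Let dPre and dPost be a subject's B-minus-A differences in pre-game and post-game gain, r their correlation, and k = SD(dPost)/SD(dPre). Ranges: r from 0 to 0.95; k = 0.8, 1.0 and 1.3. Two-sided 5% level for power.

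**Formulas** (in units of the variance of dPre, before dividing by n)

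- Change score: 1 + k² − 2rk.
- Adjusted, large sample: k²(1 − r²).
- Adjusted, n = 18 with an order term and one estimated slope: k²(1 − r²) × (1 + 1/14) = k²(1 − r²) × 15/14.

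Since 1 + k² − 2rk = k²(1 − r²) + (1 − rk)², the large-sample adjusted variance never exceeds that of the change score, and equals it only when the slope rk is 1. At n = 18 the worst case is therefore a variance ratio of 15/14 = 1.071, or √1.071 = 1.035 in standard error, whatever the value of k.

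**Equal SDs (k = 1).** The variance ratio is (1 + r)/2 × 15/14. For r = 0.5: 0.75 × 1.0714 = 0.804, and √0.804 = 0.896. Break-even: (1 + r)/2 = 14/15, so r = 13/15 = 0.87. Equivalent n is 18 divided by the variance ratio.

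| r | SE ratio, k = 1 | Equivalent n, k = 1 | SE ratio, k = 1.3 | SE ratio, k = 0.8 |
|---|---|---|---|---|
| 0 | 0.732 | 33.6 | 0.820 | 0.647 |
| 0.3 | 0.835 | 25.8 | 0.929 | 0.733 |
| 0.5 | 0.896 | 22.4 | 0.988 | 0.782 |
| 0.7 | 0.954 | 19.8 | 1.030 | 0.820 |
| 0.8 | 0.982 | 18.7 | 1.034 | 0.828 |
| 0.9 | 1.009 | 17.7 | 0.991 | 0.807 |
| 0.95 | 1.022 | 17.2 | 0.896 | 0.746 |

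**Where adjustment loses at k = 1.3.** Setting k²(1 − r²)/14 = (1 − rk)² gives 1.811r² − 2.6r + 0.879 = 0, so r = 0.55 and 0.89. Between these the adjusted standard error is larger. The peak is at r = 1/1.3 = 0.77, where the variance ratio is 1.07.

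**Simulation check.** Simulated crossovers with 9 subjects per order agreed with the formulas. Both estimates were unbiased without carry-over. In runs of 100,000 replicates at k = 1, type I error was about 5% for both. Where the change score has 80% power, the adjusted analysis had about 97%, 92%, 88%, 83%, 81% and 79% at r = 0, 0.3, 0.5, 0.7, 0.8 and 0.9.

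**Carry-over.** Suppose the first paradigm shifts the second session's pre-game gain unequally, so that mean dPre is 0.25 SD, while the true post-game difference is 0 (k = 1). The change score then averages −0.25 and the adjusted estimate −0.25r: −0.08, −0.13 and −0.20 at r = 0.3, 0.5 and 0.8. If the same shift also persists in full into the post-game gain, the change score averages 0 and the adjusted estimate 0.25(1 − r), which is 0.125 at r = 0.5. Neither analysis is safe in both cases.

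**The case against.** Item 9 is a lay summary, and speaking of a change in gain there states a question without fixing an estimator. A reader might infer that the plan commits to a raw post-minus-pre analysis. It does not: absolute or percent change is not specified, a power transformation is allowed, and no B-versus-A test is named. This stands, and it is why the remedy belongs in item 10. The adjusted model is compatible with item 9.

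The gain may also be small. Pre and post values come from one session of about an hour with head-mounted eye tracking. A set-up or calibration error shared within the session would push the slope towards 1, where subtraction works well. Variation between people in response to the paradigm could make the post-game SD the larger one, and adjustment can then lose at moderate correlations. Both arguments stand. They rule out promising a smaller standard error, but the loss is capped at about 3.5%.

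Finally, this is an unpowered pilot and the change score is a valid analysis. That stands too, and limits the point to an improvement. It does not remove it: item 11 says the data are to support an application for a larger trial, which a tighter estimate serves.

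**Conclusion.** The point holds as a cheap improvement. The B-versus-A analysis is unspecified, the covariate is implied by the design, and using it usually gives a smaller standard error for the same difference. The balance is uneven: at equal SDs the reduction is 27% at r = 0 and 2% at r = 0.8, against a loss of at most about 3.5% at any SD ratio.

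Three stronger readings are not supported. First, a reader might infer that adjustment always helps, or loses only at correlations of about 0.9 or more. That threshold depends on equal pre and post SDs; at a ratio of 1.3 the loss region is roughly r = 0.55 to 0.89. Second, the two analyses estimate the same difference only if there is no differential carry-over into the second session's pre-game gain, and the plan says only that sessions are on different days. Third, nothing here was calculated for DVA, so the point does not extend to it.

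The sizes rest on assumed correlations and SD ratios and on 9 completers per order.

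**What to change.** In item 10, before the data are seen, specify for each primary gain (passive and active):

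- Regress each subject's B-minus-A post-game gain difference on the B-minus-A pre-game gain difference, with an order (period) term coded +1/−1. The effect of B minus A is the intercept, that is, the value at a pre-game difference of zero. The covariate must not be centred at its sample mean, because the intercept would then be the unadjusted mean post-game difference.
- Report the B-minus-A difference in change scores, with the same order term, as a sensitivity analysis.
- State that a material difference between the two estimates will prompt consideration of carry-over into the second session's pre-game gain.

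Item 9 can stay as it is. The cost is a few lines of wording, one degree of freedom (15 instead of 16) and a possible loss of at most about 3.5% in standard error. No extra subjects or measurements are needed.

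### Does the Aim 2 pre/post comparison need a rule for how the four weekly sessions enter it?

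*Combined protocol and SAP*

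**What the plan says.** In the combined protocol and SAP, Section 3, item 9 gives the Aim 2 schedule, "Each subject will play once a week for four weeks", and follows it with "This will give us preliminary data regarding short-term VOR learning in these patients". Section 4, item 22 confirms the count: "Vestibular patients who are the subjects of Aim 2 will each participate for four sessions".

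Section 3, item 10 names passive and active VOR gain as the primary outcomes, calculated per subject and condition, and gives the pre/post test for the study as a whole: "Pre- and post-adaptation VOR gains will be compared using a paired t-test".

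Section 3, item 13 states that Aim 2 "will obtain preliminary data regarding efficacy and feasibility of the game for clinical vestibular therapy" and describes its procedure as like that of Aim 1. On measurement it says "The active and passive VOR, as well as DVA, will be recorded before and after the game". On the setting it says "For each subject, we will begin by determining the baseline VOR gain", with scene motion then placed 20% above that value for each head direction (worked example: 0.5 to x0.6). Difficulty is held constant during the game "because in clinical rehabilitation the difficulty is advanced more slowly, in a series of sessions over weeks of therapy".

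Item 11 calls the study an unpowered pilot meant to support a funding application for a larger trial. Item 14 records no control group. Item 20 stops Aim 2 enrolment at 6 unilateral and 6 bilateral patients with complete data.

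**The concern.** A paired t-test needs one pre value and one post value per patient. If VOR is recorded around the game at every session, each patient supplies four such pairs per outcome and head direction, and nothing says which pair is used or how they are combined. An analyst could take the change within a session (first session only, or the mean of four) or the change from before week 1 to after week 4. These answer different questions. The first measures what one sitting achieves. The second mixes that with whatever was retained between weeks.

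Two consequences seem to follow. If the scene-motion setting is held, patients who retain more have less left to learn in later sessions, so the four-session mean falls and good carry-over reads as poor learning. And if the 48 pairs (12 x 4) were pooled as though independent, the test would be too liberal. Because the results are meant to inform a larger trial, an effect size that depends on an unstated choice looks like a weak planning input.

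**Working it through.** The plan gives no effect size, SD, alpha or power for Aim 2, so there is no figure to reproduce. Three checks apply: what the text supports, how far the contrasts differ, and what a sensible default does.

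**1. What the text supports**

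- Item 13 places VOR recording around the game, and the game is played at each session.
- Item 13 models the Aim 2 procedure on Aim 1, where each paradigm occupies a single session and gain change belongs to that session.
- Item 8 uses the term short-term for Aim 1 adaptation, which happens within a session. Item 9 uses it for learning in Aim 2.
- The remark in item 13 about weeks of therapy explains why difficulty is not advanced during the game. It does not define an outcome.

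Within-session change has direct support. A week-1-to-week-4 contrast is possible but is not named as an endpoint.

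**2. How far the contrasts differ**

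From item 13: starting gain 0.5, setting x0.6. Assumed, not in the documents: a fraction a of the gap to the setting is closed in each session, and a share r of each session's change is kept to the next week. For session k:

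- c_k = a(target_k - pre_k)
- post_k = pre_k + c_k
- pre_(k+1) = pre_k + r c_k

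With a = 1, r = 0.5 and the setting held at 0.6, c = 0.100, 0.050, 0.025, 0.0125. The mean is 0.1875/4 = 0.047. Week-1-pre to week-4-post is 0.6 - 0.5 = 0.100. Week-1-pre to week-4-pre is 0.5 x (0.100 + 0.050 + 0.025) = 0.088.

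Results for a = 1, in the order mean within-session / week-1-pre to week-4-post / week-1-pre to week-4-pre:

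| r | Setting held at x0.6 | Setting re-set to 20% above current gain |
|---|---|---|
| 0 | 0.100 / 0.100 / 0 | 0.100 / 0.100 / 0 |
| 0.25 | 0.068 / 0.100 / 0.058 | 0.108 / 0.195 / 0.079 |
| 0.5 | 0.047 / 0.100 / 0.088 | 0.116 / 0.299 / 0.166 |
| 1 | 0.025 / 0.100 / 0.100 | 0.134 / 0.537 / 0.364 |

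Three readings of the table:

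- The first-session change is 0.100 in every row. With the setting held it equals the week-1-pre to week-4-post change at every r. So it is not true in general that within-session and cross-week change agree only when nothing is retained. The gap arises for the four-session mean, or when the setting is re-set.
- At r = 1 the second figure is the sum of the four changes and the first is their mean. The ratio of 4 is an identity and says nothing about patients.
- With the setting held, week-1-pre to week-4-post is 0.100 whether retention is nil or complete, so it cannot show carry-over. Week-1-pre to week-4-pre can: it runs from 0 to 0.100.

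**3. What a sensible default does**

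A simulation of 100,000 runs with 12 patients and four sessions (assumed two-sided 0.05 level) gives these type I error rates:

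| Correlation of session changes (assumed) | 48 pairs pooled | One mean per patient |
|---|---|---|
| 0 | 0.051 | 0.050 |
| 0.1 | 0.084 | 0.049 |
| 0.3 | 0.156 | 0.050 |
| 0.5 | 0.220 | 0.049 |
| 0.7 | 0.278 | 0.050 |

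Pooling would do harm, but the plan does not ask for it, and pairing by patient is the ordinary reading of a paired t-test.

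On precision, assume independent measurement error of SD s per gain value. The per-patient standard error is sqrt(2/4)s = 0.71s for the four-session mean and sqrt(2)s = 1.41s for a single week-1-to-week-4 difference. Multiplying by 2.201/sqrt(12) gives 95% half-widths of 0.45s and 0.90s for 12 patients, counting measurement error only. The mean is tighter, while a cross-week difference speaks to the whole course.

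**The case for a change.** The strongest case for acting is that favouring within-session change does not finish the job. The analyst must still choose between session 1, the mean of four, and separate tests by session, and could do so after seeing the data. The sentence on short-term learning follows directly on the four-week schedule, so it could refer to the whole course, and item 13 does speak of efficacy for therapy. Once some learning carries over, the four-session mean and the cross-week change generally differ, whatever the exact retention. Stating the choice would take a few sentences.

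Much of this stands. The number of contrasts is open, and so is whether the baseline is determined once or at each session, on which the contrasts from session 2 onward depend. What does not follow is a correction. A request to name a primary contrast, without saying which, replaces no rule that gives a wrong result. The choice is also a trade-off between precision and the question answered. In a pilot with no alpha and no decision tied to a p-value, a choice made late costs little if change is shown for every session, because a reader can then form any of the contrasts.

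**Conclusion.** The omission is genuine but is missing detail that analysts fill sensibly. The natural analysis is one value per patient, such as the mean within-session change, with change shown by session. Any comment on retention would rest on week-1-pre to week-4-pre. All of this comes from the same recordings, provided VOR is measured around the game at each session, as item 13 implies.

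The size of the discrepancy is illustrative only. At r = 0.5 with full adaptation, the week-1-pre to week-4-post change is 0.100/0.0469 = 2.1 times the four-session mean with the setting held, and 0.2986/0.1160 = 2.6 times with it re-set. Both ratios rest on adaptation and retention fractions that the documents do not supply. Whether the baseline is taken once or weekly is left open in item 13, and this review proposes neither. No change to the plan is called for. The eventual report should label which contrast each Aim 2 figure represents and note that none has a control group.
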